4.2 Design Diagram

This is a Phase 3, double-blind, randomized, multicenter study of higher versus standard adalimumab dosing regimens for induction and maintenance therapy in subjects with moderately to severely active UC (Mayo Score of 6 to 12 points with an endoscopy

subscore of 2 or 3, confirmed by a central reader). For all Mayo Score evaluations throughout the study, the stool frequency and the rectal bleeding subscores will be calculated based on entries recorded in daily electronic patient diaries.

The study was designed to enroll 840 subjects (504 subjects in the higher induction dose regimen and 336 subjects in the standard induction dose regimen) at approximately 125 sites for the main study and 100 subjects (60 in the higher induction dose regimen and 40 in the standard induction dose regimen) at 21 sites for Japan Sub-Study to meet scientific and regulatory objectives without enrolling an undue number of subjects in alignment with ethical considerations. Therefore, if the target number of subjects has been enrolled, there is a possibility that additional subjects in screening will not be enrolled.

This study will include:

An up to 21 days Screening Period

[figure not shown]
An 8-Week Double-Blind Induction Study

A 44-Week Double-Blind Maintenance Study

A 70-Day Follow-Up Period

During both the Induction Study and the Maintenance Study, visit week designations will represent weeks since first adalimumab dose in the Induction Study. Week 0 (Baseline) will reflect the date of first adalimumab dosing in the Induction Study. Week 8 will represent the final assessment in the Induction Study and the beginning of the Maintenance Study. Week 52 will represent the final assessment in the Maintenance Study (representing 44 weeks of maintenance treatment in the Maintenance Study). A subject's participation in the study is anticipated to be up to 65 weeks. There is a \pm 3 day window for all study visits. An effort will be made to bring subjects back to their original scheduled visit (calculated from Baseline) if they are out of the visit window.

A schematic of the study design is presented in [Figure 1](#).

Figure 1. Study Schematic

Screening Period

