Since subjects do not always adhere to the study visit schedule, the following rules will be applied to assign actual visits to protocol-specified visits including early termination visits. For each study visit mentioned in the protocol, a nominal or target day along with a window around the target day will be selected to represent the corresponding visit. Windows will be selected in a non-overlapping fashion so that a date collected on the CRF does not correspond to multiple visit windows. Moreover, windows will not discard

any post-baseline measurement recorded on the CRF. If a subject had two or more actual visits in one visit window, the visit closest to the target will be used as the study visit for that window. If two visits are equidistant from the target, then the later visit will be used for reporting. If more than one assessment is collected on the same day, then the average of those assessments will be used in analyses.

Table 1. Visit Windows for Analysis of Efficacy Variables, Laboratory Parameters and Vital Signs (Induction Study)

Scheduled Week	Nominal Day	Time Window (Rx Day A Range)
Week 0 ^a	1	≤ 1
Week 1	8	2 – 11
Week 2	15	12 – 22
Week 4	29	23 – 43
Week 8 ^a	57	44 – 71 ^b

Rx Day A = date of visit – date of first study drug injection in the Induction Study + 1

a. hs-CRP and fecal calprotectin collections are scheduled at Screening/Week 0 and Week 8 per protocol.

b. Minimum of Day 71 or the date of the first injection in the Maintenance Study, if applicable.

Table 2. Visit Windows for Analysis of Endoscopy Variables (Induction Study)

Scheduled Week	Nominal Day	Time Window (Rx Day A Range)
Week 0	1	≤ 1
Week 8	57	2 – 71 ^a

Rx Day A = date of visit – date of first study drug injection in the Induction Study + 1

a. Minimum of Day 71 or the date of the first injection in the Maintenance Study, if applicable.

Table 3. Visit Windows for Analysis of IBDQ, SF-36 and WPAI (Induction Study)

Scheduled Week	Nominal Day	Time Window (Rx Day A Range)
Week 0 ^a	1	≤ 1
Week 2	15	2 – 22
Week 4	29	23 – 43
Week 8 ^a	57	44 – 71 ^b

Rx Day A = date of visit – date of first study drug injection in the Induction Period + 1

- a. SF-36 and WPAI collections are scheduled at Week 0 and Week 8 per protocol.
- b. Minimum of Day 71 or the date of the first injection in the Maintenance Study, if applicable.

Definition of Missing Data Imputation

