The following imputation methods will be used to impute missing values in the efficacy analyses. In addition, an observed case analysis will be performed.

Non-Responder Imputation (NRI)

The NRI approach is used for binary efficacy variables. These variables can take values of 'Achieved' or 'Not Achieved,' or may be missing for any reason including discontinuation from study. According to the NRI imputation approach, all missing value will be considered as 'Not Achieved.' In addition, subjects who prematurely discontinue from the study drug will be considered as 'Not Achieved' for all subsequent visits after discontinuation.

Observed Case (OC)

The OC analysis will not impute values for missing evaluations, and thus a subject who does not have an evaluation on a scheduled visit will be excluded from the OC analysis for that visit. In addition, the OC analysis will not use values after premature discontinuation of study drug.

Mixed-Effect Model Repeated Measure (MMRM)

The repeated measure analysis will be conducted using mixed model including observed measurements at all visits. Data collected after premature discontinuation of study drug will be excluded from the analysis. The mixed model includes the categorical fixed effects of treatment, visit and treatment-by-visit interaction, stratification factors at randomization, and the continuous fixed covariates of baseline measurement. An unstructured variance covariance matrix will be used.

Last Observation Carried Forward (LOCF)

The LOCF rule will be used to impute for missing continuous and categorical efficacy data. Baseline and Pre-Baseline values will not be used to impute the missing Post-Baseline values. Missing values after Study Day 1 will be imputed using the latest non-missing value after Day 1 and prior to the missing value. If there are no non-missing values after Baseline, then the LOCF value will be missing. If a subject has missing values for a specific visit, the data will be imputed using LOCF only for the period which the subject started.

Rules for Calculation of Stool Frequency Subscore and Rectal Bleeding Subscore

The diary entries on the days the subjects take endoscopy preparation medications, the day of endoscopy procedure, and 2 days after endoscopy procedure will be excluded. For the calculation of the stool frequency subscore and the rectal bleeding subscore at each visit, the most recent 5 available diary days from up to 14 days preceding the visit will be used.

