To calculate these subscores when fewer than 5 days of diary data are available in the previous 14 days, the average will be based on the most recent 4 days will be used if only 4 days are available, or the average will be based on the most recent 3 days will be used if only 3 days are available.

If the subject has fewer than 3 days of diary entries, the score for that subject at the visit will be considered missing, and the subject will be categorized as a non-responder (NRI) for any categorical endpoints relating to data for this visit.

Rounding to one decimal place will be applied to the calculation above for the subscores, Partial Mayo Score and Full Mayo Score.

The last day of the 5 days will be used to decide the actual visits that should be assigned to the Mayo Score and Partial Mayo Score data.

Rules for Efficacy Assessment Based on Concomitant Treatment

Subjects in whom the UC-related systemic or rectal corticosteroids that were not being taken at Baseline and are initiated during the study or who have dosages of these medications increased to greater than the dose taken at Baseline will be censored for efficacy assessments (i.e., will be considered non-responders for categorical endpoints and will have last non-missing values carried forward for non-categorical assessments) from that point through the end of the study. These subjects will continue to be evaluated in the safety population.

The equivalent steroid dose will be determined based on [Table 4](#):

Table 4. Equivalent Steroid Dose

Corticosteroid	Equivalent Dose (mg)
Cortisone	25
Hydrocortisone	20
Prednisone	5
Prednisolone	5
Triamcinolone	4.0
Methylprednisolone	4.0
Betamethasone	0.75
Dexamethasone	0.75
Budesonide	1
Beclomethasone	5

Definition of Medication Use at Baseline

Medications are considered to be used at Baseline if the medication start date is on or before the first study drug dose date and the medication end date is on or after the first study drug dose date. All medications with a start date after the first study drug dose date or an end date before the first dose date are excluded.

Treatment Interruption

If the study drug treatment interruption is longer than 60 days and treatment re-introduction is evaluated as not feasible, the subject will be considered as premature discontinuation from the study in all efficacy assessment after the last dose and all the aforementioned imputation rules apply.

Imputation of Missing Dates

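### Mayo scores are placed in visit windows by the last diary day, so a compliant Week 2 visit on Day 12 loses its score to Week 1

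*SAP*

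**What the plan says.** Section 6.0 of the Induction SAP and section 6.0 of the Maintenance SAP carry the same set of rules.

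- **Diary days.** For the stool frequency and rectal bleeding subscores at a visit, "the most recent 5 available diary days from up to 14 days preceding the visit will be used". Around an endoscopy, the preparation days are left out, and "the day of endoscopy procedure, and 2 days after endoscopy procedure will be excluded" (Induction SAP; the Maintenance SAP is equivalent). At least 3 usable days are required.
- **Date of the score.** "The last day of the 5 days will be used to decide the actual visits that should be assigned to the Mayo Score", and likewise the Partial Mayo Score.
- **Date used by the windows.** The footnote to Table 1 in the Induction SAP reads "Rx Day A = date of visit – date of first study drug injection in the Induction Study + 1". The Maintenance footnote also starts from the visit date.
- **Two records in one window.** "the visit closest to the target will be used as the study visit for that window"; if they are equally distant, the later one is used.
- **Missing binary outcomes.** Under non-responder imputation, "all missing value will be considered as 'Not Achieved".

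Section 4.2 of both SAPs allows a plus or minus "3 day window for all study visits".

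**The concern.** One score has two candidate dates. Table 1 is built around visit days, but the scoring rule enters it with a diary day that is always earlier than the visit. A visit near the lower edge of its window can therefore have its score filed under the previous visit. The true visit is then empty: a failure for binary endpoints, and absent from the observed-case and MMRM analyses. The moved score either goes unused or displaces the previous visit's own score. If it goes unused, that also sits badly with the statement in section 6.0 that the windows discard no post-baseline measurement.

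At stake are mainly the additional endpoints in section 10.4 of each SAP: Partial Mayo remission and response over time, Mayo subscores over time, and time to Partial Mayo response or remission.

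**Working it through.** **Inputs.** Induction Table 1: Week 1 nominal Day 8, window 2–11; Week 2 nominal Day 15, window 12–22; Week 4 window 23–43; Week 8 nominal Day 57, window 44–71. Maintenance Table 1: lower window edges 23 (Week 12), 107 (Week 24), 198 (Week 37) and 296 (Week 52); nominal Rx Days 29, 113, 204 and 309. Visit allowance ±3 days. Last diary day = visit day − 1 with a complete diary and no endoscopy.

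**Induction Week 2.** The allowance permits Days 12–18.
- Visit on Day 12: last diary day 12 − 1 = 11, which lies in Week 1.
- If the Week 1 visit was on Day 8, its last diary day is 7, which is |7 − 8| = 1 day from target. The moved score is |11 − 8| = 3 days from target, so it is not used.
- If the Week 1 visit was on Day 5 or 6, its last diary day is 4 or 5, which is 4 or 3 days from target. The moved score then wins, outright or as the later of two equidistant records, and replaces the Week 1 score.
- In every case Week 2 has no score.

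The reason is simple. Days 8 and 15 have their midpoint at 11.5, so Week 2 has 3.5 days of room below its target. An early visit (3) plus the minimum diary lag (1) uses 4.

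**Other induction visits, complete diary.** Only a visit on the first day of a window (12, 23 or 44) moves. Days 23 and 44 are 6 and 13 days early, outside the allowance.

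**Maintenance, complete diary.** Visits are scheduled from Baseline, so Rx Day = nominal + visit deviation − dose delay. With the visit 3 days early and the first maintenance dose 3 days late:

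| Week | Rx Day of visit | Last diary day | Window it falls in |
|---|---|---|---|
| 12 | 29 − 6 = 23 | 22 | Week 10 (2–22) |
| 24 | 113 − 6 = 107 | 106 | Week 22 (79–106) |
| 37 | 204 − 6 = 198 | 197 | Week 35 (170–197) |

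At each of these weeks this is 1 of the 49 combinations of the two deviations (7 × 7). No other week moves.

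**Share of Week 2 scores displaced.** The documents give no attendance pattern, so these are assumptions. A visit on day *d* moves if Days 12 to *d* − 1 are all unusable. With probability *q* that a diary day is missed, P = Σ p(d)·q^(d−12) over d = 12,…,18.
- Uniform attendance: *q* = 0 gives 1/7 = 14.3%; *q* = 0.15 gives 16.8%.
- Triangular attendance (weights 1, 2, 3, 4, 3, 2, 1 over 16): *q* = 0 gives 1/16 = 6.25%; *q* = 0.15 gives 8.6%.

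Of the 840 + 100 = 940 planned subjects, that is 940 × 0.0625 ≈ 59 to 940 × 0.168 ≈ 158 displaced scores. Only would-be achievers are wrongly failed. Taking the Week 8 planning rates in section 4.3 as an illustration for Week 2, response of 50% gives about 29–79 subjects. Remission of 0.6 × 35% + 0.4 × 20% = 29% gives about 17–46.

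**Primary endpoints.** If endoscopy preparation takes 2 days (assumed) and the exclusions end the day before the visit, the last usable day is visit − 6.
- Week 8: earliest on-schedule visit Day 54; 54 − 6 = 48 ≥ 44. It stays.
- Week 52: earliest Rx Day 309 − 6 = 303; 303 − 6 = 297 ≥ 296. It stays.
- Day 54 with Days 44–53 unusable (10 days): the look-back is 40–53, leaving 40–43. Four days are usable, so the score is evaluable, but its last day is 43 and it goes to Week 4.
- Rx Day 303 with 296–302 unusable (7 days): usable days 289–295 remain, and the score goes to Week 48.
- Rx Day 309 with 296–308 unusable: the look-back is 295–308, so one day is left. The score is already missing under the 3-day minimum, whichever date is used.

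**The case against.** The best defence is a different reading. The sentence speaks of actual visits, the term the window rules use for clinic attendances before they are mapped to scheduled ones. The last diary day might only tie a diary average to an attendance, which is then windowed by its own date as the Table 1 footnote says. On that reading nothing moves. It is possible but strained: the look-back is already taken for a known visit, so the sentence would have no work to do. At the least, the text allows two programmers to reach different data sets.

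Other parts of the defence stand. The window boundaries are ordinary midpoints between nominal days and are not themselves at fault. The maintenance cases need two extremes together. The endpoints are additional ones outside the ranked sequence, and the Induction SAP plans no formal tests and no multiplicity adjustment. The rule is the same in both blinded arms, and nothing in the documents shows a differential effect.

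Three stronger inferences are tempting and are not supported:
- A reader might infer that the primary analyses are at risk. They are reached only with long runs of unusable diary days at early visits, and not at the nominal Week 52 visit.
- A reader might count every displaced score as a wrongly failed subject. Non-achievers are not achieved either way.
- A reader might infer that diary subscores part from the physician's global assessment and endoscopy of the same visit. The sentence assigns the composite scores as units, so the text does not show this.

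**Conclusion.** The rule is badly fixed in both SAPs and should be corrected. Read plainly, it moves the score of a compliant Week 2 visit on Day 12 with a complete diary into Week 1 and leaves Week 2 as a failure. The effect is about 6–17% of Week 2 scores displaced under the assumed attendance patterns. If displacement is unrelated to arm and outcome, the Week 2 response and remission rates, and their differences between arms, are multiplied by about 0.83–0.94. In Maintenance, with complete diaries, it is confined to one extreme combination of timings at Weeks 12, 24 and 37. The Week 8 and Week 52 primary endpoints are not affected for on-schedule visits with complete diaries.

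This rests on three further assumptions: the visit-day diary entry is not used, as the look-back wording indicates; Partial Mayo is collected at Weeks 1 and 2, as Table 1 suggests (the visit schedule is not at hand); and the subscores over time take the same date as the composite. The rule also names 5 days and does not say what happens when only 3 or 4 are used.

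**What to change.** In section 6.0 of both SAPs, replace the sentence with:

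*Stool frequency and rectal bleeding subscores, and the Partial and Full Mayo Scores built from them, are assigned to the analysis window of the clinic visit for which the diary look-back was taken, using the date of that visit.*

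Leave the 14-day look-back and the 3-day minimum as they are. This agrees with the Table 1 footnotes, keeps a visit on Day 12 in Week 2, and covers scores based on 3 or 4 diary days. The cost is one sentence per SAP and a different date variable in the derivation. No new data are needed.

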7.1 Demographic and Baseline Characteristics

For the subjects in I-ITT and J-ITT for Induction Study, demographic information and baseline values will be summarized by descriptive statistics. Categorical data will be summarized by frequency and percentage; and quantitative data will be presented by n, mean, standard deviation, minimum, median, and maximum values.

The following demographic and baseline values will be summarized.

Continuous Variables:

Age [years]

Body weight [kg]

Height [cm]

Body mass Index [kg/m²]Blood Pressure (systolic/diastolic) [mmHg]Pulse (bpm)Respiratory rate (RPM)Temperature [°C]IBDQ scoreFull Mayo score and its components (stool frequency, rectal bleeding, PGA, and endoscopy subscores)Partial Mayo scoreAdapted Mayo scorehs-CRP (mg/L)Short Form 36 Health Survey (SF-36) and its componentsWPAI and its componentsAlbumin (g/L)Disease duration**Categorical Variables:**Sex [male/female]Race [White, Black/African American, Asian, American Indian/Alaska Native, Native Hawaiian/Other Pacific Islander, Multirace]Ethnicity [Hispanic/Latino, Japanese, None of these]Tobacco use [user, ex-user, never used, unknown]Alcohol use [drinker, ex-drinker, non-drinker, unknown]Baseline hs-CRP (< 5 mg/L and > 5 mg/L)Disease extent (disease limited to rectum, left-sided, extensive/pancolitis)Prior infliximab use (yes, no)Region (US versus non-US)

7.2 Medical History

Medical and Surgical History: A complete medical and surgical history (which includes UC-onset date) and history of tobacco and alcohol use will be obtained from each subject during the Screening Period. Medical history will be summarized using body system and condition/diagnosis for J-ITT analysis set for Induction by treatment group. No statistical tests will be performed.

Chest X-Ray Results: All subjects undergo a standard chest x-ray of chest (including a posteroanterior (PA) and lateral view) at Screening Period. Number and percent of subjects with presence or absence of finding for the previous TB infection, calcified granulomas, pleural scarring/thickening, and other findings will be presented for J-ITT analysis set by treatment group. No statistical tests will be performed.

TB Test Results: Results of PPD skin test or QuantiFERON-TB Gold test at screening visit will be summarized for J-ITT analysis set. If PPD skin test is performed, induration will be summarized descriptively using n, mean, standard deviation, minimum values, median, and maximum values. The frequency distribution of induration ≥ 5 mm and < 5 mm will be provided. No statistical tests will be performed.

ECG Results: ECG results at screening will be presented for J-ITT analysis set as frequency distribution showing results as Normal, Abnormal (Not clinically significant), Abnormal (Clinically significant) and Unable to evaluate/missing. No statistical tests will be performed.

7.3 Previous Treatment and Concomitant Medications

Prior medications include all medications taken prior to the first dose of study drug. This includes medications with a start date before the first study drug administration date, regardless of the end date of these medications. Medications taken on the day of the first dose of study drug are not counted as prior medications.

Concomitant medications include medications with a start date prior to the Baseline date which are continuing after Baseline and all medications with a start date between the Baseline date and last study drug administration + 14 days or until first dose of maintenance study drug, whichever is earlier. All medications with an end date prior to the first dose date are excluded. If the start date is completely missing for a medication and if the stop date is before the baseline date, it is considered previous medication and not further evaluated. In addition to start date being completely missing, if the stop date is also completely missing or the stop date is on or after the baseline date, it will also be considered as a concomitant medication.

Based on generic medication names, these categories of medications used by subjects before and during the study will be summarized by counts and percentages for J-ITT analysis set for Induction Study by treatment group. No statistical tests will be performed.

The number and percentage of subjects using immunosuppressants (defined as azathioprine, 6-mercaptopurine, or methotrexate), and anti-TNF therapies at any time prior to baseline will be tabulated. Similarly, the use of oral corticosteroids, immunosuppressants (defined as azathioprine/6-mercaptopurine/methotrexate), oral aminosalicylates, and anti-TNF therapies at baseline will be tabulated.

8.0 Patient Disposition

Subject disposition will be present for subjects in the I-ITT and J-ITT analysis set for Induction Study using the following information by treatment group:

Number and percentages of subjects in various analysis sets by treatment group and by investigator and/or site number

Number and percentages of subjects completing Week 8 visit and discontinuing on or before Week 8 visit

Number and percent of subjects who prematurely discontinued the study (on or before Week 8) by primary reason and by any reason

Summary of protocol deviations will be provided.

9.0**Study Drug Exposure and Compliance**

Study drug exposure and compliance will be summarized for the I-ITT and J-ITT analysis set using the mean, standard deviation, minimum, median, and maximum. Exposure to study drug (total patient-years) will be summarized by treatment group for the Induction Study.

The number of injections received at each schedule time point will be summarized with frequencies and percentages for each treatment group for the Induction Study.

Study Drug Exposure (in Days) during the Induction Study

For subjects who discontinued from the Induction Study:

Date of last dose of Induction Study drug – Date of first dose of Induction Study drug + 14 days

For subjects who completed the Induction Study:

Date of first dose of Maintenance Study drug – Date of first dose of Induction Study drug

The date of last dose of Induction Study drug is defined as the date of last study drug injection before the date of re-randomization into Maintenance Study. The date of first dose of Maintenance Study drug is defined as the date of first study drug injection on or after the date of re-randomization into Maintenance Study.

Study Drug Compliance:

Treatment compliance will be summarized for each treatment group in the ITT population. The treatment compliance is defined as the number of injections actually taken by the subject divided by the number of injections planned to be taken by the subject during the Induction Study.

